## 9.1 Definition of Baseline and Change from Baseline

In general, the last non-missing measurement prior to the first study treatment administration will be used as the baseline measurement. If an assessment is performed on the same day as the start of treatment it will be assumed that it was performed prior to it and will be considered as baseline. Since enrollment is planned up to the second treatment week of the first treatment year, baseline data collected will occur retrospectively. This is according to the study design since the decision to prescribe the treatment should be prior to study enrollment. Administration of Patient questionnaires such as HRQoL and Disability Assessments may be administered after cladribine administration if enrollment occurs after treatment administration. For those cases, baseline measurement will be the data collected at the Baseline visit.

Absolute and percent changes from baseline are defined as

absolute change = visit value – baseline value percent change =  $100 \times \text{(visit value - baseline value)/baseline value}$ 

## 9.2 Study Day / Study Treatment Day

Day 1 is the day of the start of study treatment, the day before is Day -1 (no Day 0 is defined). Study day/Study treatment day is defined relative to Day 1.

#### 9.3 Definition of Duration and 'time since' Variables

Duration in days will be calculated by the difference of start and stop date + 1 (e.g. length of follow-up (Months) = End of Study date – date of Cladribine treatment + 1) if not otherwise specified. For events that are "ongoing", the duration will be calculated based on the date of the last contact instead of the date of death.

The time since an event (e.g. time since the first diagnosis) will be calculated as reference date minus date of the event.

#### 9.4 Conversion Factors

The following conversion factors will be used to convert days into months or years:

1 week = 7 days, 1 month = 30.4375 days, 1 year = 365.25 days.

## 9.5 Windowing and Unscheduled Visits

As this is a non-interventional study, study assessments are part of the routine practice and related data will be collected during the visits in line with the Summary of Product Characteristics and as clinically indicated. Patients will attend the sites as per routine practice at the discretion of the treating physician. Therefore, the timing of the visits is an approximation.

The first visit will be the Baseline visit. Patients who meet all eligibility criteria and who sign the Informed Consent Form (ICF) can be enrolled in the study. Inclusion can occur at the time point of treatment prescription with Cladribine tablets up until the second treatment week of the first treatment year. Baseline data will be collected at the time of the visit.

In addition to the baseline data, data collection is planned at 4 supplementary visits according to routine practice: at months 6 (Visit 1), 12 (Visit 2), 18 (Visit 3) and 24 approximately (Visit 4).

Apart from Baseline visit, PROs assessments will be derived considering a 6 months ( $\pm$  30 days) frequency and will be calculated using study day as shown in table below:

Visit Name	Derivation
Baseline	Baseline visit a
Months 6 (Visit 1)	150 days ≤ STUDY DAY ≤ 210 days
Months 12 (Visit 2)	335 days ≤ STUDY DAY ≤ 395 days
Months 18 (Visit 3)	510 days ≤ STUDY DAY ≤ 570 days
Months 24 (Visit 4)	700 days ≤ STUDY DAY ≤ 760 days

<sup>a Baseline visits will not be remapped as the starting of the observation and will be assigned as per eCRF visit.

Out of windows data will be included in a sensitivity analysis for HRQoL.

As per the study design, the definition of unscheduled visits does not exist. According to the instructions provided to the sites, when more than 1 appointment occurs within a time-period (e.g. 6-Months), only the appointment closer to the upper limit of that visit will be recorded in the eCRF.

## 9.6 End of Study, Date of last Contact and Lost to Follow-up

End of study is defined as the last visit performed by the patient within the period of 24-Months  $\pm$  3 months after baseline.

A patient will be considered lost to follow-up when he/she prematurely discontinued the study, meaning that he/she discontinued the study prior to finalizing the 24-Months observational period. As per the protocol and eCRF options, a patient can be lost to follow-up due to:

- Withdrew consent from study
- Death
- Change to other DMD
- Other reason (e.g. not able to contact the patient)

As per the study design, discontinuation of treatment does not imply lost to follow-up. Patients who discontinue the treatment will continue to be followed for safety reasons until the 24-Months observational period ends or unless they switch to another DMD treatment.

The date of the last contact will be derived as:

- End of study date, for patients completing the observational period
- Date of death for patients lost to follow-up due to death
- Maximum of the following event dates, when complete dates available, for lost to follow-up patients when lost to follow-up cause is not death:
  - o Maximum available date of visit.
  - Study drug start
  - o Adverse Event (AE) start and end dates
  - o Concomitant Medication (CM) start and end dates
  - o Date of Quality of Life (QoL) questionnaires (MSIS-29, CCI and Treatment Satisfaction Questionnaire for Medication [TSQM]).

Only dates associated with patient actual examinations reported in the eCRF will be used in the derivation. Dates associated with a technical operation unrelated to patient status such as the date a blood sample was processed will not be used.

#### 9.7 Definition of On-treatment Period

The on-treatment period is defined as the date of the first dose of study treatment to the date of the last contact. Due to the posology and long-term effects of Cladribine, a patient is on-treatment from the first dose received of Cladribine until the follow-up period ends.

## 9.8 Imputation of Missing Data

Unless specified otherwise in other IAP sections, all data will be evaluated as observed, and no imputation method for missing values will be used.

Treatment dates are not expected to be incomplete as they are required fields in the eCRF and no partial dates are allowed. Specific rules for classification of AEs and CMs for analysis purpose are presented below.

Missing statistics, e.g. when they cannot be calculated, should be presented as "nd". For example, if n=1, the measure of variability (SD) cannot be computed and should be presented as "nd".

#### 9.8.1 TEAE classification

Rules presented in Table 1 will be used for classification of AEs as Treatment-Emergent Adverse Events (TEAEs). An AE is considered a TEAE if started on or after study treatment start date.

Table 1 TEAE Classification rules

Start date of AE		Start date of AE	TEAE classification
Day	Month	Year	
UNK	UNK	UNK	TEAE
UNK	UNK	< Treatment start (year)	Not TEAE
UNK	UNK	≥ Treatment start (year)	TEAE
UNK	UNK < Treatment start (month and year)		Not TEAE
UNK	≥ Treatment start (month and year)		TEAE
< Treatment start (complete date)		(complete date)	Not TEAE
≥ Treatment start (complete date)		(complete date)	TEAE

AE = Adverse event; TEAE = Treatment-emergent adverse event; UNK = Unknown

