9.2.2 Definition of Study Cohorts and Description of Treatments

This is a single cohort study enrolling all patients that switch to Cladribine tablets from first-line DMDs, according to the decision of the treating physician. Patients should have been under treatment with first-line DMDs for at least one year prior to switching (see Section 9.2.1) and should have been prescribed to Cladribine tablets prior to enrollment (baseline visit). Enrollment may take place from the time of cladribine prescription up until the second treatment week, in the first treatment year.

All eligible patients are treated with Cladribine tablets in routine clinical practice. Patients will receive Cladribine as per the SmPC and the discretion of their treating physician. According to the SmPC, each treatment course consists of 2 treatment weeks, one at the beginning of the first month and one at the beginning of the second month of the respective treatment year. Each treatment week consists of 4 or 5 days on which a patient receives 10 mg or 20 mg (one or two tablets) as a single daily dose, depending on body weight. If necessary, the treatment course in Year 2 can be delayed for up to 6 months to allow for recovery of lymphocytes (at least 800 cells/mm³). If this recovery takes more than 6 months, the patient should not receive Cladribine tablets anymore. In patients where cladribine tablet treatment was delayed, follow-up will remain 2 years after enrollment and will not be extended by the period by which treatment was delayed.

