11.4 Recording of Adverse Events

The recording period for AEs begins, when the subject is initially included in the study (date of signature of first informed consent) and continues at least end of the mandatory safety-follow-up period at last study visit. However, as enrollment may take place from the time of cladribine prescription up until the second treatment week, in the first treatment year, any ADRs assessed as related to cladribine by the Investigator after the first dose of cladribine but before signature of Informed Consent must be recorded in the eCRF as well.

All adverse events, as specified above, occurring during the study, must be documented by the Investigator in the eCRF, including its description, seriousness, severity (grading), duration (onset

and resolution dates), causal relationship, any other potential causal factors, actions taken with the study drug (e.g. dose reduction, withdrawal), required treatment and outcome of the AE.

Note - Event term 'Death', 'Disability' and 'Hospitalization'

Death, disability, and hospitalization are considered outcomes in the context of safety reporting and not usually considered ARs/AEs. Therefore the primary cause of death, disability or hospitalization should be recorded and reported as an SAE/AR, and the outcome should be recorded in a separate data field. However, a term for the outcome will be selected if it is the only information reported or provides significant clinical information.

If death occurs, the primary cause of death or event leading to death should be recorded and reported as an SAE. "Fatal" will be recorded as the OUTCOME of this respective event and not be as separate event. Only, if no cause of death can be reported (for example, sudden death, unexplained death), the death per se might then be reported as an SAE.

Reports of Special Situations (see definition) are also to be recorded in the CRF following the AE procedure, even if occurring without AE.

Pregnancy and Breastfeeding. Pregnancy or breastfeeding must be recorded in the CRF and additionally be reported to the Sponsor immediately (within 24 hours of awareness) by using separate paper data collection forms for pregnancy, independent if an AE was reported or not. The outcome of the pregnancy should be followed up and reported to the Sponsor until delivery.

Women who become pregnant under therapy with Cladribine tablets should discontinue treatment.

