#### 15.1 Adverse Events

The TEAE are those events with onset dates occurring within the on-treatment periods as defined in Section 9.7.

The AEs related to study treatment are those events with relationship missing or "Related".

All analyses described in Section 15.1 will be based on TEAEs if not otherwise specified. The AE listings will include all AEs (whether treatment-emergent or not). AEs outside the on-treatment period will be flagged in the listings.

Unless otherwise specified, TEAEs will be summarized by number and percentage of patients with the TEAE in the category of interest, primary SOC and PT in decreasing frequency.

Each participant will be counted only once within each SOC or PT. If a participant experiences more than one AE within a SOC or PT for the same summary period, only the AE with the strongest relationship or the worst severity, as appropriate, will be included in the summaries of relationship and severity.

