#### 15.1.1 All Adverse Events

The AEs will be summarized using the latest version of MedDRA PT as event category and MedDRA primary SOC body term as body system category.

Incomplete AE-related dates will be handled as specified in Section 9.8.1.

The following tables will be created

- TEAE summary table with the number and percentage of patients having:
  - o TEAE
  - TEAE of Special Interest (TEAESI)
  - TEAE leading to death
  - o TEAE leading to Cladribine dose reduction
  - o TEAE leading to Cladribine temporary discontinuation
  - o TEAE leading to Cladribine permanent discontinuation
  - TEAE leading to study termination
  - TEAE not recovered/resolved
  - Any serious TEAE:
    - TEAESI
    - Leading to death
    - Leading to Cladribine dose reduction

- Leading to Cladribine temporary discontinuation
- Leading to Cladribine permanent discontinuation
- Leading to study termination
- Not recovered/resolved
- Cladribine related TEAE:
  - TEAESI
  - Serious
  - Leading to death
  - Leading to Cladribine dose reduction
  - Leading to Cladribine temporary discontinuation
  - Leading to Cladribine permanent discontinuation
  - Leading to study termination
  - Not recovered/resolved
- Incidence of TEAE by Primary SOC and PT
- Incidence of Serious TEAE by Primary SOC and PT
- Incidence of Serious TEAE related to Cladribine by Primary SOC and PT
- Incidence of TEAE leading to Cladribine temporary discontinuation Primary SOC and PT
- Incidence of related TEAE leading to Cladribine temporary discontinuation Primary SOC and PT
- Incidence of TEAE leading to Cladribine permanent discontinuation Primary SOC and PT
- Incidence of related TEAE leading to Cladribine permanent discontinuation Primary SOC and PT
- Incidence of TEAE leading to death by Primary SOC and PT
- Incidence of related TEAE leading to death by Primary SOC and PT
- Incidence of TEAE by Primary SOC and PT and relationship to Cladribine
- Incidence of TEAE by Primary SOC and PT and severity
- Incidence of TEAESI by Primary SOC and PT and severity
- Incidence of TEAESI by Primary SOC and PT and by relationship to Cladribine

2.0

• Incidence of Serious TEAESI by Primary SOC and PT and by relationship to Cladribine

All AEs regardless of being treatment-emergent or not will be listed.

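### SAP Table 1 classifies adverse events on start date alone, so an incompletely dated event whose recorded stop date is before the first cladribine dose is still counted as treatment-emergent

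*SAP*

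**What the plan says.** The definition in SAP 9.8.1 concerns onset only: "An AE is considered a TEAE if started on or after study treatment start date". The same section makes Table 1 the operative rule: "Rules presented in Table 1 will be used for classification of AEs as Treatment-Emergent Adverse Events (TEAEs". The table's only inputs are the parts of the AE start date. An event is a TEAE when:

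- the start is wholly unknown;
- only the year is known, and it is the year of treatment start or later;
- only the month and year are known, and they are those of treatment start or later.

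No row looks at the stop date or at whether the event is ongoing.

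The rest of the SAP does not change this. SAP 15.1 states "The TEAE are those events with onset dates occurring within the on-treatment periods as defined in Section 9.7", and SAP 9.7 fixes that period: "The on-treatment period is defined as the date of the first dose of study treatment to the date of the last contact". SAP 15.1.1 sends incomplete dates back to the same table: "Incomplete AE-related dates will be handled as specified in Section 9.8.1".

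Two protocol provisions allow an event to fall before the first dose. Protocol 11.4 says "The recording period for AEs begins, when the subject is initially included in the study (date of signature of first informed consent"), and Protocol 9.2.2 says "Enrollment may take place from the time of cladribine prescription up until the second treatment week, in the first treatment year". Consent, and with it AE recording, can therefore precede dosing.

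**The concern.** Counting an event of uncertain onset as treatment-emergent is a sound default. The difficulty is that Table 1 applies the default even when a recorded stop date has removed the uncertainty. If an event ended before the first dose, its onset was before the first dose, however little is known of the start date. Table 1 still returns TEAE, which is the opposite of what the section's definition gives. This is a written rule with a wrong result, not a detail left to programming.

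At stake is the accuracy of the TEAE tables. This is a single cohort with no comparator, so a pre-dose event counted in those tables has nothing to offset it. Several TEAE tables are also on the interim output list in SAP 18.2, so the rule would operate there as well as in the final analysis.

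**Working it through.** The plan gives no figure to reproduce on this point. The check is to apply Table 1 as written to example records, then to apply it again with a stop-date condition placed ahead of it.

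**Inputs**

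- Rule: SAP 9.8.1, Table 1.
- Stop date collected: the items that Protocol 11.4 requires for each event include onset "and resolution dates), causal relationship, any other potential causal factors, actions taken with the" study drug.
- Stop date available to the analysis: SAP 9.6 uses AE end dates to derive the date of last contact.
- Treatment start always complete: SAP 9.8 says treatment dates are required fields with no partial entries.
- Planned enrolment: 242 (Protocol 9.5).
- Assumed for illustration: first dose 20 June 2021.

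**Classification of example records**

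| AE start | AE stop | Table 1 as written | With stop-date condition |
|---|---|---|---|
| wholly unknown | 10 Jun 2021 | TEAE | Not TEAE |
| 2021, month and day unknown | 10 Jun 2021 | TEAE | Not TEAE |
| Jun 2021, day unknown | 10 Jun 2021 | TEAE | Not TEAE |
| May 2021, day unknown | 10 Jun 2021 | Not TEAE | Not TEAE |
| 2020, month and day unknown | 10 Jun 2021 | Not TEAE | Not TEAE |
| 5 Jun 2021 | 10 Jun 2021 | Not TEAE | Not TEAE |
| Jun 2021, day unknown | 1 Jul 2021 | TEAE | TEAE |
| Jun 2021, day unknown | unknown | TEAE | TEAE |

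Only the first three patterns change. In each of them the stop date proves that onset was before treatment. Partial starts in an earlier month or year are already handled correctly, and onsets that remain ambiguous stay TEAE.

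**Which patients can be affected.** The record must fall between consent and first dose. For a patient who enrols after the first dose, which Protocol 9.2.2 permits, that interval does not exist. The one exception in Protocol 11.4 for events before consent covers reactions after the first dose, so it cannot supply a pre-dose event.

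**Size per patient.** 1/242 = 0.0041, or 0.41 percentage points in any row where the patient is wrongly counted. The number of such records is not in the documents. Assuming 0 to 3 patients, all in the same row, the range is 0 to 3/242 = 1.24 percentage points. The denominator is planned enrolment; a smaller FAS would raise these figures slightly.

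**The case against.** The best case for leaving the table alone is that the default is conservative. It can add events to cladribine but cannot remove one, so no signal would be missed. The affected record is also rare. It needs consent before dosing, an incomplete start date, and a stop date known to precede the dose. SAP 6 provides for a data review meeting and resolution of queries before lock, where such a record could be noticed, and SAP 15.1 lists all AEs whether treatment-emergent or not. All of this stands, and it limits the importance of the point. It does not correct the rule. The listings flag events outside the on-treatment period, but for an incomplete start date Table 1 is the only stated rule, so the flag would presumably carry the same error.

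A reader might infer more than the documents support, in two ways.

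- **That events on the previous DMD or during washout are reported as treatment-emergent.** AE recording starts at consent. Protocol 11.1 excludes conditions present at study start that do not worsen. Inclusion criterion 4 in Protocol 9.2.1 requires any necessary washout to have been done already. Most such events therefore never enter the database as AEs.
- **That a rare special-interest row could show a false signal.** Protocol 11.1 and 11.5 put these events through the SAE procedure, with 24-hour reporting, corroborating detail and follow-up to stabilisation or known outcome. Malignancies are pathologically confirmed and severe lymphopenia is defined by laboratory values, so a date would normally exist. Such an event would also have to begin and end between consent and first dose. The documents give no reason to expect this.

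**Conclusion.** The point holds as a small error in the classification rule. For three patterns of incomplete start date, Table 1 counts as treatment-emergent an event whose recorded stop date shows that it was not, against the definition in the same section. No other section of the SAP overrides it.

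The effect is an over-count of about 0.4 percentage points per affected patient in any row concerned, and it cannot run the other way. The number of affected patients is unknown and may be zero. The conclusion rests on reading Table 1 as the complete rule, as SAP 15.1.1 indicates, and on some patients consenting before their first dose, as Protocol 9.2.2 allows. The effectiveness analyses are not touched. It is worth correcting because the correction is almost free, not because the safety results are in doubt.

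**What to change.** Add one row to SAP Table 1, ahead of the partial-date rows:

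> If the AE stop date is known to be before the treatment start date, the AE is not a TEAE, whatever is known of its start. This applies when (a) the stop date is complete and earlier than treatment start; (b) the stop day is unknown and the stop month and year are strictly earlier than those of treatment start; or (c) only the stop year is known and it is strictly earlier than the year of treatment start. In all other cases, including a partial stop date in the same month or year as treatment start, or an unknown stop date, apply the rows below.

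The strict inequalities matter. A stop date known only to the month or year of treatment start does not settle whether the event ended before the dose, so it must stay with the existing default.

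The cost is one row in the SAP and one condition in the program. Stop dates are already collected and treatment dates are always complete, so no new data, query type or CRF change is needed. The adjacent Table 2 for concomitant medications already looks beyond the start date by using ongoing status, so the addition fits the plan's own approach.

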Patients will be enrolled consecutively at study sites in the participating countries. Each patient will be followed for the course of their standard Cladribine treatment (approximately 2 years according to clinical practice).

Figure 1 provides a schematic overview of the study design. Figure 2 provides an overview of the patient journey within the study. Enrolment may take place from the time of cladribine prescription up until the second treatment week, in the first treatment year.

[figure not shown]
[figure not shown]

Figure 1 - Schematic of Study Design³

³ Pts: patients: IFN: Interferon; DMF: Dymethyl fumarate; DMD: Disease Modifying Drug

* Interferon, Glatiramer Acetate, Teriflunomide, DMF

Figure 2 - Study Patient Journey

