9.1.2.2 Secondary

- Difference in ARR between the pre-baseline 12-month period and over the 12 months period after the start of cladribine (1 year)
- Percentage of patients with 6-month disability progression⁵ at the end of the study followup period (2 years), measured as EDSS, T25FW (optional) and 9-HPT (optional).

⁴ Relapses will be diagnosed by the treating physicians, as per routine clinical practice; a typical definition within this context is the appearance of new symptoms of the exacerbation of pre-existing symptoms that are attributed to MS and occur over a minimum of 24 hours and separated from a previous attack by at least 30 days, in the absence of fever or infection.

⁵ Disability progression is defined as progression on ≥1 of 3 components (EDSS, T25FW, and/or 9HPT) confirmed ≥24 weeks apart and with a ≥20% minimum threshold change for T25FW and 9HPT, Progression on EDSS is defined

L04AA40 MS700568 0070

Cladribine

- Percentage of patients with 6-month disability improvement⁴ at the end of the study followup period (2 years), measured as EDSS, T25FW (optional) and 9-HPT (optional)
- · Occurrence of adverse events and of serious adverse events
- Quality of life (MSIS-29)
- Treatment Satisfaction (TSQM v1.4)
- CCI
- Treatment adherence, assessed as percentage of cladribine tablets taken versus prescribed dose

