9.3 Variables

- Demographic data: Gender, age, race (if allowed as per local regulation)
- Other Baseline Assessments: Weight
- Medical history, including MS, malignancies, severe and opportunistic infections
- MS-Medication history: DMD, immunosuppressive/immunomodulatory agents (other than DMD, such as corticosteroid treatment)
- Therapy with Cladribine Tablets [date of administration and number of tablets taken versus prescribed dose (treatment adherence)]
- Reason for switching from first line DMD to Cladribine Tablets
- Participation in a Cladribine Patient Support Program
- Course of disease
 - o Relapses
 - o MRI data
 - T2, T1 Gd+ and CUA lesion counts
 - o EDSS Score
 - o T25FW (time in seconds, optional)
 - o 9-HPT (time in seconds, optional)
- TSQM-v1.4 VAS score
- MSIS-29 score

- · EQ-5D-3L score
- Safety (Serious Adverse Events (SAEs), Adverse Events of Special Interest (AESI) and Adverse Drug Reactions (ADRs))

Derived and transformed data needed for the analysis are described in Section 9.7.2.

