The Investigator will ensure any necessary additional therapeutic measures and follow-up procedures are recorded and reported via a follow-up report form. For all serious cases/ADRs/fatal cases and special situations and AESIs missing information such as outcome, confounders, and causality is to be provided. Additionally, follow-up information of non-serious adverse drug reactions may be required by the Sponsor for medical assessment. Reasonable attempts to obtain follow-up information must be made and documented.

Reporting of any new information on a previously reported event (follow-up) will follow the procedures and timelines of the original report.

CRO should forward the follow-up information within 24 hours to Global Patient Safety, as noted above for initial reports. The sponsor has to meet strict regulatory timelines associated with expedited safety reporting obligations.

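### TEAEs are defined by onset date alone, so an AE that starts before the first dose and worsens after it under its original record is left out of the SAP 15.1 tables

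*SAP*

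**What the plan says.** **Classification.** SAP 9.8.1 gives the rule: "An AE is considered a TEAE if started on or after study treatment start date". In its Table 1, a complete start date earlier than treatment start leads to the class Not TEAE. SAP 15.1 puts the same test in other words: "The TEAE are those events with onset dates occurring within the on-treatment periods as defined in Section 9.7". SAP 9.7 opens that period at the first dose. None of these places mentions an event that was already present and became worse.

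**Use.** Analyses under SAP 15.1 rest on TEAEs unless stated otherwise, and no table listed in 15.1.1 states otherwise. The AE listings hold all AEs and flag those outside the on-treatment period. The SAE tables in SAP 15.2.2 are not labelled treatment-emergent.

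**Recording.** Protocol 11.4: "The recording period for AEs begins, when the subject is initially included in the study (date of signature of first informed consent"). Protocol 9.1.1: "Enrolment may take place from the time of cladribine prescription up until the second treatment week, in the first treatment year". For each AE, Protocol 11.4 asks for seriousness, severity, onset and resolution dates, and causality, among other items. It gives no instruction for a change in severity.

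**Scope of collection.** The protocol is not uniform. Section 9.3 lists "Safety (Serious Adverse Events (SAEs), Adverse Events of Special Interest (AESI) and Adverse Drug Reactions (ADRs"), while the secondary outcome in 9.1.2.2 is "Occurrence of adverse events and of serious adverse events". Protocol 11.4 also reads broadly.

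**The concern.** A treatment-emergent count should include an event that was mild before the first dose and became severe after it. Under a pure onset-date rule, whether that event is counted depends on how the site keeps the record. If the worsening is entered as a new AE with its own date, it is a TEAE. If the existing record is updated, it is not. The same clinical course can therefore fall in or out of the tables according to site habit.

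The omission runs one way: it can only lower the reported TEAE incidence. Safety is a stated secondary objective, and its reported percentages come mainly from the SAP 15.1 tables. The SAP does foresee the parallel case for medications. SAP 9.8.2 allows one that started before treatment and is still ongoing to count as both previous and concomitant. The AE rule next to it has no such provision.

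**Working it through.** The plan gives no figure to reproduce. The check is a reading of the rules, followed by a scale for the effect.

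**1. Does the gap exist?** Yes, for patients who consent between prescription and first dose. Patients enrolled after their first dose have no such interval.

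**2. Table 1 applied to a hypothetical patient.**

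| Event | Date |
|---|---|
| Consent | 1 March |
| Mild AE begins | 5 March |
| First cladribine dose | 10 March |
| Same AE becomes severe | 20 March |

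With one record and onset 5 March, the complete start date precedes treatment start, so the class is Not TEAE. The event is absent from every SAP 15.1 table and appears, flagged, in the listing. If the worsening is entered as a new AE with onset 20 March, it is a TEAE. The result needs a known onset date: Table 1 treats a wholly unknown date, or a partial date falling in the month or year of treatment start, as a TEAE.

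**3. Does other text restore the event?**
- The worst-severity rule in SAP 15.1 works within analyses already limited to TEAEs, so it cannot bring back an event classed as Not TEAE.
- Protocol 11.5 says: "Reporting of any new information on a previously reported event (follow-up) will follow the procedures and timelines of the original report". This makes updating the old record plausible, but it governs safety reports and does not settle the eCRF entry.
- Protocol 11.1 removes from the AE definition only baseline conditions that do not worsen. It implies that a worsening is reportable but sets neither a new record nor a new onset date.
- SAP 9.5 mentions instructions to sites: "According to the instructions provided to the sites, when more than 1 appointment occurs within a time-period". They concern which visit to enter, not AE records.

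**4. Scale from the documents.** Planned enrolment is 242 (Protocol 9.5).
- One patient: 1/242 = 0.41 percentage points.
- Patients needed to move an incidence by one point: 0.01 × 242 = 2.42, so 3.

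The actual denominator is the treated patients, who may be fewer than 242.

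**5. Illustration.** Every input except 242 is an assumption. The documents give no AE rate, no consent-to-dose time and no information on record-keeping.

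Events lost = 242 × f × r × (w/365.25) × s × k

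| Input | Assumed value |
|---|---|
| f, share consenting before first dose | 0.75 |
| r, AEs per patient-year | 1 |
| w, days from consent to dose | 30 |
| s, share worsening after dosing | 0.10 |
| k, share kept under the old record | 0 to 1 |

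- AEs starting in the gap: 242 × 0.75 × 1 × 30/365.25 = 14.9.
- Of these, worsening: 14.9 × 0.10 = 1.5.
- Lost: 0 at k = 0; 0.75 events (0.31 points) at k = 0.5; 1.5 events (0.62 points) at k = 1.

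The formula is a product, so doubling any one input doubles the result. These figures apply if all AEs are collected. If only SAEs, AESIs and ADRs are collected, the loss is close to nil: no cladribine ADR can precede the first dose, and SAEs keep a route to the 15.2.2 tables. A patient already counted for another TEAE does not change the overall incidence at all.

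**The case against.** The strongest reply is that the loss turns on something the two documents do not show. Whether a worsening opens a new record is usually settled in eCRF completion guidelines, and those may already require it. This stands. The point is that the SAP rule is safe only if such an instruction exists, not that events are known to be lost.

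A second reply is that the onset rule is explicit and consistent across SAP 9.7, 9.8.1 and 15.1, and that the plan leans towards counting elsewhere: uncertain dates count as TEAEs, and a missing relationship counts as related. This is true, but it does not reach a pre-dose event with a complete date.

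Third, the protocol partly points to a post-dose onset. SAP 9 takes cladribine start as the study start date. Read with Protocol 11.1, a condition present at first dose that later worsens could be an AE from that time. This is a fair reading, but no onset date is prescribed.

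A reader might infer that the related-TEAE and AESI tables are equally exposed. The documents do not support that. Protocol 11.1 defines an ADR as a response to a medicinal product, and Protocol 11.3 weighs AE onset against drug administration, so a worsening attributed to cladribine would naturally carry a post-dose onset. Lymphopenia becomes an AESI only at Grade 3 or above, and its duration runs from the severe finding, so a milder pre-dose count is not yet that event.

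**Conclusion.** The point holds as a minor one. By the SAP's own rule, an AE that starts between consent and first dose, worsens after dosing and keeps its record and onset date is left out of the SAP 15.1 tables. Neither document prevents this. The loss is mainly of non-serious events, because a serious one can still enter the 15.2.2 tables and all AEs stay in the listings.

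The size cannot be derived from the documents. It is 0.41 points per affected patient, and the illustration stays below one point even when every worsening is kept under the old record. It rests on three conditions: consent before the first dose, a known pre-dose onset date, and sites updating existing records.

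A reader might go further and conclude that reported safety is materially understated. Nothing here supports that. Safety is descriptive, the count affected is probably very small, and it may be zero if site guidelines already ask for a new record.

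**What to change.** **SAP text.** In 9.8.1 and 15.1, extend the definition so that an AE is also treatment-emergent if it *was present before the first dose and worsened in severity or became serious on or after it*.

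**Site instruction.** Ask sites to enter a worsening as a new AE with the date of worsening as its onset. Table 1 then applies unchanged to new records. If the eCRF guidelines already say this, refer to them in the SAP.

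**Records already entered.** List every AE with onset before the first dose that was ongoing at that dose, not only the serious, related or special-interest ones. Ask the site whether it worsened and when. The date of worsening is not among the AE fields named in Protocol 11.4, so it has to come from a query. Set the TEAE flag at the data review meeting that SAP 6 already plans before lock, and record it as an exception to Table 1.

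**Cost.** One clause in two SAP sections, one instruction, one review list and a few site queries. No new assessments or patients are needed. TEAE incidence may rise slightly.
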